Multiple lines of evidence and our preliminary data indicate that resistance training (RT) could be an ideal addition to CR+AT for HFpEF.(184) (1) RT reliably increases muscle mass, quality, strength, and function, significantly more than AT,(37) and specifically during CR.(36; 50; 74; 76; 77; 101; 144; 184; 225) We found that in older non-HF patients undergoing CR, RT reduced loss of lean mass by 47%, and enhanced body composition and physical function(198) - nearly identical to Frimmel et al who found that RT reduced loss of muscle mass by 48%.(74) (2) In HFpEF, RT improves exercise capacity independent of cardiac function and to a similar degree as AT.(177) In older men, RT significantly increased peak VO₂ (+1.9 ml/kg lean/min) and was associated with increased type 1 fiber area, thigh muscle area, capillary density, and citrate synthase (all of which we have found deficient in HFpEF).(76; 77) (3) RT and AT can have additive effects on peak VO₂(20; 49; 144) In HFpEF, the addition of RT to AT doubled the training-related increase in endurance.(20) (4) RT also improves peak VO₂ by mechanisms independent of muscle mass, including muscle mitochondrial function, blood flow, inflammation, and neuromuscular function.(50; 76; 77; 103; 201; 207; 226) Muscle mitochondrial function is a fundamental driver of peak VO₂ and is reduced in older persons and in HFpEF,(50; 76; 77; 104; 201; 207; 226) and is improved by RT in HFpEF.(226) In diabetics, addition of RT to AT improves muscle mitochondrial content, function and oxidative capacity, resulting in increased peak VO₂.(201) Our preliminary data (Sections 3.D.4.) suggest that: a) muscle mitochondrial content is reduced in HFpEF, and b) is related to the increase in peak VO₂ following CR+AT; c) mitochondrial respiratory function is reduced in obese older adults, and d) improves with RT. (5) RT and AT have complementary effects on muscle and cardiovascular function.(52; 92; 95; 101; 103; 144; 157) (6) Regimens adding RT to AT improve compliance.(50; 225) These data provide a strong rationale for the addition of RT to AT during CR.

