However, RT has never been tested with CR in any type of HF. Furthermore, there are few data regarding RT in HFpEF; a pilot study used a small dose of RT in combination with AT,(58) and another small study included just 3 HFpEF patients.(177) Although initial concerns have been largely allayed regarding the potential effect of RT on left ventricular (LV) function in HFpEF,(135) there remains equipoise in HFpEF. RT can significantly increase arterial stiffness

and LV hypertrophy(153; 225) a potential concern in HFpEF patients who often already have increased arterial stiffness and LV hypertrophy.(106; 124; 137; 230) Therefore, it is important to rigorously test the efficacy and safety of adding RT to CR+AT, as we propose here using state-of-the-art methods.

Objectives

The **primary** aim is to conduct a randomized, controlled, single-blinded 20-week intervention trial of RT added to CR+AT in 84 overweight / obese (BMI \geq 28 kg/m²), older (age \geq 60 years) HFpEF patients to test the following primary hypothesis:

- **The addition of resistance training to CR+AT will improve peak VO₂.**

The **secondary** aims of the study are to test the following secondary hypotheses:

- **Resistance training added to CR+AT will improve retention of skeletal muscle mass.**
- **Resistance training added to CR+AT will improve skeletal muscle mitochondrial function.**
- **The improvement in peak VO₂ with RT will be related to improved skeletal muscle mass and mitochondrial function, and accompanied by improved QOL.**

Peak VO₂ (ml/min) will be assessed by expired gas analysis. Skeletal muscle mass will be measured as thigh muscle area by MRI and total lean mass by DXA.(94; 100) Mitochondrial function and indices of cell death will be assessed by respirometry, protein expression analyses, and enzyme activity assays.(23; 24; 209) QOL will be assessed by the KCCQ instrument. Muscle strength and quality, and cardiac and vascular function will also be assessed.

Methods and Measures

Design

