Confidence in our estimates is enhanced because they are based on data from our recently completed factorial trial of CR and AT using the same patient population and primary outcome. The chosen sample size has adequate power for the primary and secondary aims and QOL. The effect of CR+AT on peak VO₂ was 110.8 ml/min (7.6% relative effect) with a square root of the mean square error for the ANCOVA model being 107.5. To have 90% power to detect a relative effect due to RT of 5.6% (absolute difference of 82.0 ml/min) in peak VO₂ at the 0.05 two-sided level of significance, the study requires 38 evaluable participants per group. In our recent trial, the retention rate was excellent (93%), similar to our previously published trials in HFpEF. To allow for up to 11% loss to follow-up, a total of 42 subjects per group (84 total) will be randomized. In our recently completed study, we observed a 7.4 cm² decrease in thigh muscle area measured by MRI in the CR+AT vs. control group. The square root of the mean square error was 5.98 using analysis of covariance. With 76 evaluable subjects we will have 80% power to detect if the decrease in muscle mass is reduced by 53% (e.g. a difference of 3.9 cm²). In our study of older, non-HF participants, RT had an effect of this magnitude on muscle retention during CR.(198). We will confirm muscle retention with DXA measurement of total lean mass. In our recently completed study; we observed a 2.2 kg decrease (3.2% relative effect) (square root mean squared error of 28.47) providing 80% power to detect a 2.8% relative effect of RT. This sample size also allows adequate power for the secondary aim, mitochondrial function. In our pilot study, RT increased respiratory control ratio (RCR) from 2.78 to 7.23 (160% increase; mean square error of 6.372). The sample size provides 80% power to detect a 60% increase in RCR. It also provides 80% power to detect a 10% relative difference in the KCCQ QOL score. The sample size also provides adequate power to detect increases in confirmatory measures of exercise capacity. In our recent study, we observed a 35.4%, 13.8%, and 13.9% increase in the AT+CR vs. control group in exercise time, VO₂ reserve, and six-minute walk distance respectively. The sample size provides 90% power to detect a 10%, 8%, and 6% increase in exercise time, VO₂ reserve, and six-minute walk, respectively. We will also have 80% power to detect partial correlations as low as 0.30 at the 0.05 two-sided level of significance to examine independent relationships with peak VO₂.

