Mitochondrial Mechanisms for Skeletal Muscle Loss, a phenomenon related to reduced peak VO₂ in HFrEF(3) but never examined in HFpEF, will be assessed by using: 1) expression of Bax, ICE, p53, Fas receptor protein, and cyclophilin D as indices of programmed cell death;(171) 2) Bcl-2 as an index of protection against apoptosis; and 3) calcium retention capacity and H₂O₂ emission in PmFBs as indices of susceptibility to opening of the mitochondrial permeability transition pore and mitochondrial failure.(6; 173)

Physical Activity will be assessed using two accelerometers, the Actigraph GT3X+ and the Lifecorder EX. The Actigraph monitor is a small device worn on the non-dominant wrist, and the Lifecorder monitors is a small device worn on the right hip, attached to the waistband. Both monitors assess variables related to physical activity: energy expenditure, steps, and physical activity duration, intensity, and frequency. Participants will wear both devices for 7 continuous days during baseline and follow-up testing to assess changes in physical activity pre to post intervention. There are no risks associated with wearing an activity monitor.

Study visit timeline.

Table 3. Assessment Timeline	Visit code	SV	BV1	BV2	BV3	Interv.	FV1	FV2	FV3
Activity/assessment	Week number					0-20			
Informed consent, screening, demographics, echocardiogram/Doppler, dietary interview		X							
Physical exam, medical history, medication review		X					X		
RMR, Blood draw, questionnaires, Exercise test			X				X		
SPPB, Muscle strength, DXA & MRI scans				X				X	
Muscle biopsy					X				X
Randomization and dietary education					X				

Analytical Plan

The trial is a 2-arm, randomized, parallel design to test the effect of adding RT to the regimen of CR+AT shown as most beneficial in our recent trial. Peak VO₂ (ml/min) will be the primary outcome measure using an intention-to-treat analysis. Analyses will be conducted using analysis of covariance (ANCOVA) with baseline peak VO₂, age and gender as predefined covariates. Similar analyses will be done for the secondary outcomes, skeletal muscle mass and mitochondrial function, QOL, and other outcomes. Partial correlation analysis adjusting for age and gender will be done to correlate changes in peak VO₂ with the other key outcomes of interest (muscle mass, mitochondrial function, and QOL).

Data Management

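### The planned test of how resistance training raises peak VO₂ does not require that resistance training changed the proposed mediator

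*Combined protocol and SAP*

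**What the plan says.** In Objectives, the last secondary hypothesis is that "The improvement in peak VO₂ with RT will be related to improved skeletal muscle mass and mitochondrial function, and accompanied by improved QOL". It is a statement about RT, the one component that differs between the arms; under Design, both arms receive caloric restriction and aerobic training (CR+AT).

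The Analytical Plan gives this hypothesis one analysis: "Partial correlation analysis adjusting for age and gender will be done to correlate changes in peak VO₂ with the other key outcomes of interest". The outcomes listed there are muscle mass, mitochondrial function and quality of life. Arm is not among the adjusting variables. The plan does not say whether arms are pooled, gives no mediation step, and states no rule for drawing the conclusion. RT effects on peak VO₂, muscle mass and mitochondrial function are each tested by ANCOVA in the same section, but no sentence links those tests to the correlation.

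Sample Size adds: "We will also have 80% power to detect partial correlations as low as 0.30 at the 0.05 two-sided level of significance".

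**The concern.** A correlation of changes asks whether patients whose muscle or mitochondria changed more also gained more peak VO₂. It does not ask whether RT caused either change. All patients diet and train aerobically, so differences between patients in, for example, adherence could move both measures in either arm.

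The documents make such a background relation plausible. Background, Rationale and Context reports that in the preceding trial, which had no RT, mitochondrial content was already related to the gain in peak VO₂ after CR+AT. The same section expects RT to work partly by other routes: "RT also improves peak VO₂ by mechanisms independent of muscle mass". If RT raised peak VO₂ by one of those routes and left thigh muscle area unchanged, the planned correlation could still be significant and be read as support for muscle mass as RT's mechanism.

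**Working it through.** **Inputs.** Sample Size gives 38 evaluable per arm (76 in total), two-sided 0.05, a peak VO₂ effect of 82.0 with root mean square error 107.5, and a thigh-area effect of 3.9 with 5.98. In SD units these are 82.0/107.5 = 0.76 and 3.9/5.98 = 0.65. Age and gender are partialled out (k = 2).

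**Assumptions.** The within-arm correlation r between the two changes is not given, so 0 to 0.40 is shown. Changes are taken as bivariate normal, with the ANCOVA root mean square errors as SDs.

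**The plan's own figures.** 38 per arm gives 90% power at 0.76 SD and 80% at 0.65 SD, as stated. For the correlation, power ≈ Φ(atanh(r)·√(N−k−3) − 1.96). At r = 0.30 and N = 76: 0.3095 × √71 = 2.608, and Φ(0.648) = 74% (75% by simulation, 77% by noncentral F). At N = 84 it is 79–81%. The stated 80% therefore fits all 84 randomised patients rather than the 76 evaluable. This is a side observation.

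**Case A: RT changes neither variable.** The formula gives the chance of a significant correlation: 5% at r = 0, 40% at 0.20, 74% at 0.30, 95% at 0.40. The primary test is positive in about 5% of such trials, so both occur together in about 0.05 × 0.40 = 2%, 0.05 × 0.74 = 4% and 0.05 × 0.95 = 5%.

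**Case B: RT raises peak VO₂ by 0.76 SD and leaves the mediator unchanged.** Pooling arms adds between-arm variance to peak VO₂ only: 1 + 0.763²/4 = 1.146. The pooled correlation is r/√1.146.
- r = 0.20: 0.187, power 36%
- r = 0.30: 0.280, power 68%
- r = 0.40: 0.374, power 91%

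Multiplying by about 0.90 for a positive primary approximates the joint chance: 32%, 61% and 82%. Simulation (38 per arm, age- and sex-adjusted) agrees:

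| r | A: correlation | A: correlation and primary | B: correlation | B: correlation and primary | B: three-part rule |
|---|---|---|---|---|---|
| 0 | 5% | 0.3% | 5% | 4–5% | 0.2% |
| 0.20 | 40% | 2% | 36% | 32–33% | 2% |
| 0.30 | 74–75% | 4% | 68–69% | 61–62% | 3% |
| 0.40 | 95% | 5% | 91–92% | 82–83% | 4% |

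The three-part rule requires a significant RT effect on peak VO₂, a significant RT effect on the mediator, and a significant association adjusted for arm.

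**Adding arm alone.** In Case A at r = 0.30 the rate stays at 74–75%. In Case B it rises from 68–69% to 74–75%, because arm removes variance from peak VO₂ that the mediator does not share. Using the RT arm alone (n = 38) gives Φ(0.3095 × √33 − 1.96) ≈ 43%, and that too contains no comparison with CR+AT.

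**The case against.** A reader might infer that the plan has a 75% false-positive rate when RT does nothing. The documents do not support that. The 75% is the power to detect a real association assumed to be 0.30, and Sample Size gives 0.30 as a detection limit, not as an expected background value. The rate runs from 5% at r = 0 to 95% at r = 0.40. With no RT effect the primary is usually null, which leaves no RT improvement to explain: a positive primary and a positive correlation coincide in only 2–5% of trials at r = 0.20 to 0.40.

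Nor does the mechanism conclusion rest on the correlation alone. The ANCOVAs for RT on muscle mass and mitochondrial function are planned, so a null mediator result would be reported beside it. The hypothesis is also worded as a relation, not as proof of mediation. Both points stand and limit the concern, but neither closes it. The hypothesis names the improvement due to RT, and no text says that a null mediator ANCOVA rules out the statement. A positive primary gives little protection in Case B.

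Three smaller points also stand. The preceding trial's relation is for mitochondrial content, with no coefficient; it is not shown for respiratory control ratio (RCR) or thigh area. The Background presents RT's routes as additive rather than rival. The 0.30 power sentence already says that it concerns relationships with peak VO₂, so it needs no rewording on this account.

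**Conclusion.** The concern holds in conditional form. The stated analysis can support an RT mechanism when RT has not moved the mediator, because neither arm nor the mediator's response to RT enters it. The case that matters is a real RT effect on peak VO₂ reached by another route. There, the primary and the correlation are both significant in about 32%, 62% and 82% of trials at r = 0.20, 0.30 and 0.40, against about 5% at r = 0. These figures rest on 76 evaluable patients, the planned 0.76 SD effect, pooled arms and an assumed r. The primary analysis and its conclusion are unaffected.

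**What to change.** Add a conclusion rule to the Analytical Plan. For each named mediator (thigh muscle area, RCR), state that RT's gain in peak VO₂ is related to it only if all three hold:

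1. the planned ANCOVA shows an RT effect on peak VO₂;
2. the planned ANCOVA shows an RT effect on that mediator;
3. the changes in mediator and peak VO₂ are associated after adjustment for arm, age and gender.

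Arm belongs in the third condition because, if RT moves both variables and they are otherwise unrelated (r = 0), the pooled correlation is significant in about 15–16% of trials; with arm it returns to 5%. Report the indirect effect (RT effect on the mediator times the arm-adjusted slope) with a bootstrap 95% confidence interval as a supporting estimate. Say that the three-part rule governs if the two disagree. If any condition fails, report the correlation only as an association among treated patients.

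The cost is SAP wording and a short analysis of data already planned, with no added patients or visits. The claim becomes harder to make: at the planned effects (0.76 and 0.65 SD) all three conditions are met in about 54% of trials at r = 0.30 and 29% at r = 0.20. The rule also leaves confounding of the within-arm slope, for example by adherence, so a positive result should be worded as consistent with mediation and not as proof of it.

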
Interventions

Exercise training overview. The exercise training regimens are based on our successful experience with aerobic training (AT) in 3 randomized trials in HFpEF patients,(127; 128; 156) and resistance training (RT) in 6 trials in older persons with disability due to conditions other than HF(60; 147; 148; 198) These were effective for improving peak VO₂, lean body mass, and QOL(22) and were safe. The exercises are based on ACSM and AHA guidelines for older persons and for HFrEF.(2; 65; 72; 225; 225) The AT and RT interventions are individualized and progressive in nature, beginning at a low level and increasing based on specific milestones (**Table 1**) to safely deliver an optimal stimulus. Both groups (AT-only and AT+RT) will meet 3 times per week for 20 weeks. The total *stimulus* phase of the sessions for both groups will be 50 minutes (30 min for AT and 20 min for RT). To keep the duration similar for both groups, 20 min of light chair-based range-of-motion, stretching, and flexibility maneuvers will be included at the end of the AT-only group sessions. This attention /physical activity control will provide no resistance or aerobic activity. Warm-up and cool-down phases will be 5 min each with stretching, flexibility, and light walking for a total session time of 60 min for both groups.

Table 1	AT Regimen	RT Regimen
----------------	-------------------	-------------------

Intensity	Initial: 40-50% HRR Goal: 70-80% HRR	Initial: 20-30% 1-RM Goal: 70-80% 1-RM
Amount	Initial: ~15 minutes Goal: 30 minutes	Wk 1-3: 1 set of 8-12 reps Wk 4-20: Addition of 2 nd set to volitional fatigue
Type	Walking, treadmill, cycling	6 weight machines: leg curl, leg extension, leg press, calf raise, chest press, compound row

Sessions will be conducted at the Wake Forest Clinical Research Center by Masters-level, Certified Clinical Exercise physiologists with medical supervision to ensure safety and a uniform, robust stimulus. This facility has been used for numerous clinical trials and has appropriate emergency equipment and response team, staff trained in BLS/ACLS. To eliminate potential for cross-group contamination, the 2 groups will meet at different times.

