The exercise testing, physical performance battery, health-related quality of life, body composition by DXA, and an MRI will be conducted. In addition, physical activity monitoring, basic vital signs (height, weight, blood pressure) will be collected and a review and update of medical history will be performed to check for any possible or new contraindications to exercise testing. The blood and stool sample will also be collected at this visit.

This visit should take ~2-4 hours. It may be done in 1 or 2 visits, depending on study participant desire.

SECRET II Physical Activity Sub-Study (PASS)-COSMED K5

Background

The results of our Studies Examining Caloric Restriction and Exercise Trial (SECRET I) demonstrate that 20 weeks of moderate intensity aerobic exercise (AE) together with caloric restriction (CR) was safe and efficacious for individuals with heart failure and preserved ejection fraction (HFpEF) ¹. Despite many positive changes, the AE + CR combination resulted in a significant reduction of total muscle mass in these HFpEF patients ¹. Therefore, we are currently examining the benefit of incorporating resistance exercise training (RE) to improve body composition and exercise capacity in participants with HFpEF in the SECRET II study.

Moderate intensity AE is generally prescribed at 60-80% of the patient's maximum oxygen consumption (VO_{2peak}) as this level is a safe and effective for HF patients ². Since VO_2 cannot be easily measured during AE or RE, heart rate (HR) is commonly used as a surrogate measure to regulate exercise intensity. While previous research has shown that % HR and % VO_{2peak} during AE are well correlated in clinical populations ³, this relationship has not been examined in HFpEF patients. Performing AE at a low intensity (i.e. < 60% VO_{2peak}) may fail to produce optimal physiological benefits, whereas performing AE at an intensity that is too high (i.e. > 80% VO_{2peak}) may be intolerable and potentially dangerous to these HFpEF patients. Thus, it is important to ensure that HFpEF patients are performing AE and RT in the proper range of their % VO_{2peak} to ensure their safety and to stimulate maximal physiological benefits.

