Measuring VO_2 during ambulatory AE or RT was not possible until the development of the portable COSMED K5 system (see photo below). This COSMED K5 system, obtained by the Health and Exercise Science (HES) department in 2016, can be used to measure VO_2 outside of the lab environment, while patients are performing their normal activities, and/or AE and RE. This will be the first time such a measurement/study will be performed in HFpEF patients.

In addition to examining the relationship between % VO_2 and % HR during AE and RE in HFpEF patients, the COSMED K5 allows for the direct determination of energy expenditure (i.e. kcals). In addition to measuring the energy expenditure (in kcals) during AE, we can also determine the additional energy expenditure associated with performing RE in these HFpEF patients. It's unknown if adding RE to AE will result in a significant increase in energy expenditure versus AE alone in HFpEF patients. These findings will have important implications for weight loss and body composition changes and have not been assessed in HFpEF patients.

Based on existing literature and direct experience we developed the following hypotheses;

1. The average % HR will not be significantly different that the average % VO_{2peak} during either the AT only or AT + RT sessions.
2. The average physical activity energy expenditure (PAEE) during a typical exercise session AT or AT + RT will be significantly less than the recommended 300 kcal/day.
3. AT + RT will result in significantly higher PAEE than AT alone.

Methods.

This research project would be conducted in HF patients that are already participating in the SECRET II study funded by the NIH and approved by WFUBMC IRB. Participants in SECRET II are randomly assigned to two groups; CR + AE or CR+AE+RE. The SECRET II intervention is 20 weeks and will eventually enroll up to 90 HF patients over a 4 year period.

This proposed sub-study would be conducted on 15-20 of the HFpEF patients already performing AE with/without RE in SECRET II study. All data collection for this sub-study would take place at the Health and Exercise Science Department's Clinical Research Center under the supervision of [name] and will be stored on encrypted computers and/or in locked files/offices.

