Participants in SECRET II would be asked to voluntarily participate in two experimental sessions (one near the beginning and one near the end of their 20 week intervention). For each session the participants would wear the portable COSMED K5 system while performing their normal AE \pm RE exercise session. Expired air will be collected continuously during the entire exercise session that lasts \sim 1 hr. From the expired air collected by the COSMED K5 mask, the VO₂ for each minute will be obtained and compared to HR values that are obtained from a wrist worn heart rate monitor (see photo below). This data would allow us to determine if these HFpEF patients are at the appropriate intensity levels during AE \pm RE.

Furthermore, since we will be able quantify the physical activity energy expenditure (PAEE measured in kcal) from the VO₂ values obtained during both AE and AE + RE, we can compare the two groups to determine if there are additional metabolic costs associated with RT. Finally, to determine the reliability of these measures (VO₂, HR, and kcal) we will ask the first 5 participants in the study to perform a second identical experimental session \sim 1 week after the first session.

Risks.

There are no additional risks, beyond those associated with AE and RE, for the volunteers in this sub-study. Volunteering participants will perform their "normal" AE \pm RE session as part of SECRET II while wearing the COSMED K5 mask. This mask comfortably covers the subject's mouth/nose and allows, through a one-way valve system, for normal inhalation of room air and expiration to the analyzer. If at any point the mask becomes uncomfortable to the participant, it will be removed and the experimental session will be terminated. This is the same mask the participant wears during their baseline exercise test so they will already be familiar with it.

References

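### Sub-study hypothesis 1 predicts a non-significant difference between % HR and % VO2peak; with 15-20 volunteers it should be restated as estimation of the difference and of individual agreement.

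*Combined protocol and SAP*

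**What the plan says.** The Background of the sub-study (SECRET II Physical Activity Sub-Study (PASS)-COSMED K5) explains that "heart rate (HR) is commonly used as a surrogate measure to regulate exercise intensity". It adds that the relation between % HR and % VO2peak, though well correlated in other clinical populations, has not been examined in HFpEF.

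Hypothesis 1 then states: "The average % HR will not be significantly different that the average" % VO2peak, for either session type. On size, the Methods say: "This proposed sub-study would be conducted on 15-20 of the HFpEF patients" already training in the trial, with or without resistance exercise. Each volunteer is asked for "two experimental sessions (one near the beginning and one near the end of their 20 week intervention"). VO2 is obtained minute by minute and compared with heart rate from a wrist monitor.

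The sub-study text names no test, confidence interval, agreement method, margin, standard deviation or power for this comparison. The Analytical Plan of the main trial does not cover the sub-study. % HR is not defined. The Aerobic exercise training section prescribes intensity by heart rate reserve. % VO2peak is described only as a percentage of the patient's VO2peak, without saying whether the baseline or the follow-up test supplies the denominator.

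**The concern.** The question raised in the Background is whether heart rate tracks % VO2peak in HFpEF. Hypothesis 1 makes a non-significant test the predicted result. That is the wrong kind of evidence, for two reasons.

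First, the fewer the patients and the noisier the measurements, the more easily the prediction comes true, whether or not the two quantities agree. Second, a test of two averages says nothing about individuals. Heart rate could overstate intensity in half the patients and understate it in the other half, and the averages would still match.

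The protocol describes this as the first such measurement in HFpEF. A null result could therefore be cited as support for heart rate as a surrogate when the data are compatible with a sizeable gap.

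**Working it through.** The documents give no figure to reproduce for this sub-study, so everything below is illustrative.

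**Inputs from the documents:** 15-20 volunteers in total; two session types; a two-sided 0.05 level, stated for the main trial only and borrowed here.

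**Assumptions not in the documents:** an even split, giving 7-10 patients per session type; one session per patient; a within-patient difference (% HR minus % VO2peak) with SD 8-12 points, widened to 5-15; a true mean gap of 10 points.

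**1. Chance that a real gap is non-significant.** For a paired t-test with n patients, the statistic follows a noncentral t with n-1 degrees of freedom and noncentrality (gap/SD)*sqrt(n). The probability of a non-significant result is the mass between -t(0.975, n-1) and +t(0.975, n-1).

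| n | SD 5 | SD 8 | SD 10 | SD 12 | SD 15 |
|---|---|---|---|---|---|
| 7 | 0.009 | 0.214 | 0.400 | 0.543 | 0.682 |
| 10 | 0.000 | 0.061 | 0.197 | 0.349 | 0.531 |

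The range is 6-54% at SD 8-12 and 0-68% at SD 5-15.

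**2. Equal averages with unequal individuals.** With a true mean difference of zero and normal differences, the share of patients more than 10 points apart is 2*(1 - Phi(10/SD)). This gives 0.211, 0.317 and 0.405 at SD 8, 10 and 12. A perfectly null mean is compatible with 21-41% of patients being more than 10 points apart.

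**3. What estimation would deliver at SD 10.**
- Half-width of the 95% CI for the mean difference, t*SD/sqrt(n): n=7, 2.447*10/sqrt(7) = 9.2; n=10, 2.262*10/sqrt(10) = 7.2.
- Limits of agreement: mean difference +/- 1.96*10 = +/-19.6 points.
- Half-width of the 95% CI for each limit, t*SD*sqrt(1/n + 1.96^2/(2(n-1))): n=7, 24.47*sqrt(0.1429 + 0.3201) = 16.6; n=10, 22.62*sqrt(0.1000 + 0.2134) = 12.7.

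**4. Why the two definitions belong in the restatement.**
- Percent of maximum equals percent of reserve plus (100 - percent of reserve)*(resting/peak heart rate). If resting heart rate is 50-60% of peak (assumed), 60% of reserve is 60 + 40*0.5 = 80 to 60 + 40*0.6 = 84% of maximum, and 80% of reserve is 90-92%. The metric alone moves the difference by 10-24 points.
- If peak VO2 rose by 7.6%, then 60-80% of the baseline peak is 60/1.076 = 55.8 to 80/1.076 = 74.3% of the follow-up peak, a shift of 4-6 points. The 7.6% is the CR+AT effect quoted under Sample Size from the earlier trial. It is used here as a within-patient rise, which is itself an assumption.

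**The case against.** The best reply is that the plan never says a null result will be taken as agreement. It sets no decision rule, so the harm depends on a later misreading. That is correct and limits the weight of the point. It does not rescue the hypothesis, whose predicted outcome still cannot inform the surrogate question.

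A reader might also infer that hypothesis 1 is how the sub-study will judge training intensity, because the Methods say: "This data would allow us to determine if these HFpEF patients are at the appropriate intensity levels during AE". The documents do not support that. The sentence follows the description of the minute-level VO2 and heart rate data, and the Background states its intensity range in % VO2peak. The portable system measures VO2 directly, so whether patients are in range can be read without hypothesis 1.

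Another tempting inference is that the averaging window biases the comparison. The overview of exercise training says: "Warm-up and cool-down phases will be 5 min each with stretching, flexibility, and light walking for a total session time of 60 min", and AT-only sessions add 20 minutes of chair-based work, so 5 + 5 + 20 = 30 of 60 minutes lie outside the aerobic stimulus at goal duration. But the Methods say: "Expired air will be collected continuously during the entire exercise session that lasts" about an hour, and hypothesis 1 refers to sessions. The literal reading is a whole-session average of both quantities over the same minutes, and no shift in their difference follows from that.

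The numbers can be challenged too. At SD 5 the miss rate is below 1%. Pooling all 15-20 volunteers at SD 10 lowers it to 5% (n=15) or 1% (n=20), though the hypothesis is worded by session type. Averaging two sessions correlated at 0.5-0.8 would reduce an SD of 10 to 10*sqrt(0.75) = 8.7 or 10*sqrt(0.90) = 9.5, still inside the 8-12 range. These replies stand as limits on the size, not on the logic.

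On the late-session denominator, the prescription rests on initial testing and the visit timeline places the follow-up test after the intervention. Baseline is therefore the likely choice, but it is not stated for the analysis.

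The repeat sessions in the first five participants concern reliability, a separate question, and need no change here.

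**Conclusion.** The point holds as a minor one. Hypothesis 1 predicts non-significance in a sample where non-significance is weak evidence, and a comparison of averages cannot show that heart rate tracks % VO2peak within patients. This logic does not depend on the illustrative figures.

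The size does depend on them: 6-54% for a true 10-point gap at SD 8-12, or 0-68% at SD 5-15, under an assumed even split and one session per patient. None of these inputs is documented.

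The open definitions are missing detail. They matter here because an estimated difference cannot be interpreted without them; they would not carry the point alone. Nor should a reader infer any consequence for the main trial: the sub-study is voluntary, and no primary or secondary outcome depends on it.

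**What to change.** Replace hypothesis 1 with an estimation aim. For each session type, report the mean of % HR minus % VO2peak with its 95% confidence interval and the Bland-Altman limits of agreement, by a method that allows for two sessions per patient. State that a non-significant difference will not be read as agreement.

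Before analysis, state whether % HR is of maximum or of reserve, and whether late sessions use the baseline or the follow-up peak VO2. Report the whole-session average as the hypothesis is worded; averages by exercise phase are optional. An equivalence margin is not advised, because the documents give no basis for one.

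The cost is a few sentences and a standard analysis of data already planned, with no new measurement or participants. The downside is imprecision. At an assumed SD of 10, the interval for the mean difference is about +/-7 to 9 points and the interval for each limit of agreement about +/-13 to 17 points. The result will be descriptive, but that uncertainty will be visible rather than hidden behind a non-significant p-value.
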